## **1.3.2 Malignancies with Ligand Driven Hh Signaling**

### **1.3.2.1 Colorectal Cancer**

A randomized phase II clinical trial evaluated addition of vismodegib or placebo to standard chemotherapy (mFOLFOX-6 or FOLFIRI) plus bevacizumab in patients with untreated metastatic colorectal cancer (n=199)[18]. Choice of chemotherapy regimen was based on investigator decision. The primary endpoint was improvement in progression-free survival (PFS). The study failed to meet its primary endpoint of improved PFS vs. chemotherapy + placebo (hazard ratio = 1.25 [90% CI 0.89 -1.76], p =0.28) Secondary efficacy endpoints were consistent with the primary endpoint. The TEAEs (all grades) that differed in frequency by 10% or more vs. placebo were vomiting, asthenia, weight loss, decreased appetite, dehydration, muscle spasms, and dysgeusia. Grade 3-5 TEAEs that differed in frequency by 5% or more vs. placebo were fatigue, nausea, asthenia, mucositis, peripheral sensory neuropathy, weight loss, decreased appetite, and dehydration.

### **1.3.2.2 Ovarian Cancer**

A randomized phase II clinical trial evaluated the use vismodegib or placebo as maintenance treatment for patients with ovarian cancer in second or third complete remission (n=104)[19]. The primary endpoint was improvement of PFS. The study failed to meet its primary endpoint of improved PFS vs. placebo (hazard ratio=0.79 95%CI 0.46-1.35, p=0.39). TEAEs occurring in greater than 10% of vismodegib treated patients were dysgeusia/ageusia, muscle spasms, alopecia, nausea, fatigue, constipation, abdominal pain, decrease appetite, upper abdominal pain, arthralgia, vomiting and hypomagnesemia.

### **1.3.2.3 Pancreatic Cancer**

A randomized phase II clinical trial evaluated addition of vismodegib or placebo to standard chemotherapy (gemcitabine) in patients with untreated metastatic pancreatic cancer (n=106)[20]. The primary endpoint was improvement in progression-free survival. The study failed to meet its primary endpoint of improved PFS vs. chemotherapy + placebo (HR = 0.81 95%CI 0.54 - 1.21, p=0.3) Secondary efficacy endpoints were consistent with the primary endpoint. The frequency of Grade  $\frac{3}{4}$  TEAEs reported vs. placebo (V/P) were neutropenia (32%/28%), hyponatremia (4%/15%), fatigue (13%/8%), hyperglycemia (23%/19%), elevated alanine aminotransferase (ALT; 13%/9%). TEAEs that differed in frequency by 10% or more vs. placebo were vomiting, asthenia, weight loss, decreased appetite, and dehydration.

### **1.3.2.4 Glioblastoma Multiforme**

A phase II clinical trial evaluated vismodegib treatment at 150 mg QD PO in patients with glioblastoma multiforme that was recurrent after or progressive while receiving standard treatment (n=40) [21]. The primary endpoint was improvement in PFS at 6 months. The study failed to meet its primary endpoint of improved PFS at 6 months (median PFS 1.8 months 95%CI 1.40 - 1.9 months) Secondary efficacy endpoints were

consistent with the primary endpoint. TEAE reported were abdominal infection, abdominal pain, atrial flutter, fatigue, hypophosphatemia, lymphocytopenia, and thrombocytopenia (1 patient each).

### **1.3.2.5 Gastric Cancer**

A randomized phase II clinical trial evaluated addition of vismodegib or placebo to chemotherapy (mFOLFOX-6) in patients with untreated metastatic gastric cancer (n=124)[22]. The primary endpoint was improvement in PFS. The study failed to meet its primary endpoint of improved PFS vs. chemotherapy + placebo (hazard ratio = 1.03 95%CI 0.69 - 1.55, p=0.64) Secondary efficacy endpoints were consistent with the primary endpoint. No significant differences in the rates of common grade  $\frac{3}{4}$  TEAEs ( $\geq$  5% incidence) were observed between the vismodegib and placebo arms. The rates of grade  $\frac{1}{2}$  TEAEs were comparable with no significant differences except for a higher incidence of dysgeusia in the vismodegib arm (42%/16%, p=0.003).

### **1.3.2.6 Small Cell Lung Cancer**

A randomized phase II clinical trial evaluated addition of vismodegib or cixutumumab (IMC-A12) to standard chemotherapy (cisplatin/etoposide) in patients with untreated extensive stage SCLC (n=155)[23]. The primary endpoint was improvement in PFS. The study failed to meet its primary endpoint of improved PFS vs. cisplatin/etoposide chemotherapy (hazard ratio = 1.32, p=0.21) Secondary efficacy endpoints were consistent with the primary endpoint. Grade  $\frac{3}{4}$  TEAEs reported (chemotherapy alone vs. chemotherapy+vismodegib) included anemia (25%/ 9%), febrile neutropenia (15%/13%), neutropenia (48%/47%), thrombocytopenia (22%/6%), leukopenia (46%/41%), nausea (11%/11%), vomiting (9%/6%), hyperglycemia (2%/2%), muscle weakness (4%/0%), and renal dysfunction (6%/0%)

## **2. STUDY OBJECTIVES**

### **2.1 Primary Objectives**

The primary objectives of the study are:

- a. To evaluate the efficacy of GDC-0449 in reducing KCOT size (shrinkage) in NBCCS-associated KCOT and sporadic KCOT patients following 6 to 12 months of ingestion of 150 mg/day, up to 1 year of treatment and up to 2 years of post-treatment follow-up.
- b. To evaluate the safety of this dose of GDC-0449 in these patients.

*Tumor response (reduction in tumor volume and shrinkage) will be measured by volumetric CT scan.*

*Time Frame: Efficacy will be assessed at 1 year and 2 years after the study medication is stopped. Patients will undergo evaluation for 3 years (up to 1 year of treatment and up to 2 years of post-treatment follow-up). All patients will participate in the assessment of the safety and tolerability of the study drug. Safety monitoring will capture risks related to study participation and adverse events related to the study drug.*

## 2.2 Secondary Objectives

The secondary objectives of the study are:

- a. To determine the time of response of a GDC-0449 anti-proliferative effect (i.e. tumor shrinkage) after administration of the drug up to one year or until treatment is stopped;
- b. To assay germ line *PTCH1* mutations before treatment with GDC-0449 in patients with NBCCS-associated KCOT;

If tumor removal is required, to assess tumor *PTCH1* mutations before and after treatment with GDC-0449 in NBCCS-associated KCOT and sporadic KCOT in order to determine the correlation of tumor response and the presence of tumor *PTCH1* mutation.

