## **4. MATERIALS AND METHODS**

### **4.1 Subject Selection**

#### **4.1.1 Inclusion Criteria**

Patients are eligible to participate in the study if they meet the following criteria:

- Males and females, 18 years of age and above at the time the informed consent form is signed;
- Able to understand and sign the Informed Consent Form and other necessary paperwork prior to initiation of study procedures;
- Able to communicate with the investigator/study site personnel, understand and comply with the study requirements, and willing to return for specified visits at the appointed time;
- Patients who have received prior treatment for their KCOT and with a diagnosis of recurrent (maxillary or mandibular) sporadic KCOT or NBCCS-associated KCOT (single or multiple);
- Diagnosis of KCOT will be done by past pathology report or by biopsy at the study site, if applicable;
- Willingness to consent to biopsy of the lesion, if needed;
- Willingness to delay excision of the target tumor site, unless evidence of disease progression or lack of drug tolerability;
- For female patients of childbearing potential, agreement to use two acceptable methods of birth control, including one barrier method during the study and 24 months after discontinuation of study drug;
- For males with female partners of childbearing potential, agreement to use a male condom (with spermicide) and to advise their female partners to use an acceptable method of birth control during the study and for 3 months after the discontinuation of the study drug;
- Agreement not to donate blood/blood products during the study and for 24 months after the discontinuation of the study drug;
- For males not to donate sperm products or semen during treatment and for 3 months after the discontinuation of the study drug;
- Able and willing to swallow pill;

- No malabsorption syndrome or other condition that would interfere with enteral absorption;
- At least 4 weeks since last chemotherapy, investigational therapy, radiotherapy or major surgical procedure and recovered from the first study drug administration;
- KCOT measures at least 1 cm in one dimension on pretreatment volumetric CT scan;
- No clinically significant abnormalities with clinical laboratory assessments;

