### **Biopsy and Analysis of the Tumor**

If the patient had a previous biopsy performed, a tissue slide will be obtained for study purposes and confirmation of KCOT diagnosis. If clinically indicated, an additional biopsy of the tumor will be done and if the patient agrees, the leftover tissue from the tumor biopsy will be stored for future genetic analysis related to KCOT. The storing of tumor for future genetic analysis is optional and will be stored for 10 years. These additional biopsies will be flash-frozen in liquid nitrogen (LN2) and stored in LN2 at the Bluestone Center for Clinical Research.

The future genetic testing will not include tests that can identify patients' risks for other conditions. Only users authorized by the Bluestone Center for Clinical Research and Genentech would have access to the samples. The stored samples will be labeled with the subject code, diagnosis and/or location of the sample. The linking key between subject code and subject identity will be maintained by the PI. The subject may withdraw their samples from storage and future use by providing a written request to the PI.

**Assessment of Gene Mutations and Gene Expression in Tumor Specimens:** The additional fresh-frozen tumor specimens will be subjected to gene mutation and gene expression analysis. If no additional fresh-frozen specimen is obtained, the initial biopsy samples, which are formalin-fixed, paraffin-embedded (FFPE), will be used instead.

FFPE tissue scraped from serially cut slides will be deparaffinized using Envirene reagent (Hardy Diagnostics, Santa Maria, CA, USA) before isolation of RNA using the Roche High Pure FFPE RNA Micro Kit (Roche Diagnostics, Indianapolis, IN). RNA will be extracted from fresh-frozen tissue using the High Pure RNA Tissue Kit (Roche Diagnostics, Indianapolis, IN). RNA will be reversed transcribed using the High-Capacity cDNA Reverse Transcription Kit (Applied Biosystems, Foster City, CA, USA) with random primers. PCR will be carried out using the Taqman Universal PCR Master Mix (Applied Biosystems), with the following cycling conditions: 50°C for 2 min; 95°C for 10 min; 40 cycles of 95°C for 15 s, 60°C for 1 min. qRT-PCR profiling of genes associated with KCOT will be performed. For analyses, gene expression from the genes of interest will be normalized to the average cycling threshold (Ct) of three housekeeping genes (GUSB, SDHA, and UBC).

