#### **iv. Secondary Endpoints**

Secondary analysis will quantify the proportion of patients achieving minimal clinically significant changes in their tumors and comparing that to a theoretical expectation of 5% improvement with a Fisher exact test, and the effect of the *PTCH1* mutation on tumor volume reduction will be assessed with an independent samples t-test. These analyses will use the same population as the primary endpoint.

All analyses will be done using IBM SPSS Version 21.

v. Sample size determination. Twenty subjects will be recruited. Analysis of the primary endpoint is capable of detecting changes in tumor volume in the Wilcoxon tests of approximately 1.0 and .68 SD, assuming a 2-tailed type 1 error of 5% and power of 80% and then assuming either n=10 (separate analysis of the NBCSS-associated and sporadic cohorts) or n=20 (combined analysis of both cohorts), respectively (G\*Power, v3.1).

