APPENDIX A: SCHEDULE OF STUDY ASSESSMENTS & PROCEDURES

STUDY ASSESSMENTS & PROCEDURES	SCREENING PHASE	TREATMENT PHASE (1 YEAR)											POST TREATMENT FOLLOW UP (2 YEARS)							
	BASELINE VISIT	1 MONTH POST DOSING	2 MONTH POST DOSING	3 MONTH POST DOSING	4 MONTH POST DOSING	5 MONTH POST DOSING	6 MONTH POST DOSING	7 MONTH POST DOSING	8 MONTH POST DOSING	9 MONTH POST DOSING	10 MONTH POST DOSING	11 MONTH POST DOSING	1 YEAR POST DOSING	1 MONTH POST TREATMENT	2 MONTH POST TREATMENT	3 MONTH POST TREATMENT	7 MONTH POST TREATMENT	1 YEAR POST TREATMENT	2 YEARS POST TREATMENT	DISCONTINUATION VISIT
		+/- 7 DAYS																		
Informed Consent & Screening	X																			
Review of Inclusion/Exclusion Criteria	X																			
Review of Medical Records, if applicable	X	X	X	X	X	X	X	X	X	X	X	X	X	X	X	X	X	X	X	X
Medical/Dental History	X	X	X	X	X	X	X	X	X	X	X	X	X	X	X	X	X	X	X	X
Concomitant Medications	X	X	X	X	X	X	X	X	X	X	X	X	X	X	X	X	X	X	X	X
Demographics (height, weight)	X																			
Urine Pregnancy Test, if female patient of child bearing potential		X	X	X	X	X	X	X	X	X	X	X	X	X	X	X	X	X	X	X
Serum pregnancy test, if female patient of child bearing potential	X	*	*	*	*	*	*	*	*	*	*	*	*	*	*	*	*	*	*	*
Oral Cavity Assessment (soft & hard tissues)	X	X		X			X									X	X	X	X	
Physical Exam	X	X		X			X						X							X
Clinical Laboratories	X			X			X						X							X
Genetic Testing of Blood	X												X							X
Genetic Testing of the Tumor, if biopsy on excision	X												X							X
Vital Signs (BP, HR, temperature)	X	X		X			X						X				X	X	X	X
Verification of KCOT Diagnosis	X																			
Biopsy of Tumor, if applicable	X																			
Panoramic Radiograph	X	X		X			X						X				X	X	X	X
Volumetric CT Scan	X						X						X					X	X	X
Skin Examination for NBCCS-associated KCOT patients	X						X						X					X		X
Photographs of Skin Lesions, if applicable	X						X						X					X		X
Study Drug Administration – First Dose	X																			
Study Drug Dispense until next visit / Compliance with study drug	X	X	X	X	X	X	X	X	X	X	X	X	X							
Continuance Criteria/Study Reminders		X	X	X	X	X	X	X	X	X	X	X	X	X	X	X	X	X	X	
Adverse Events	X	X	X	X	X	X	X	X	X	X	X	X	X	X	X	X	X	X	X	X
Study completion, Discharge																				X

\* Any positive urine pregnancy test must be confirmed by a serum pregnancy test.

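### Section 2.2 ties tumour PTCH1 typing to tumour removal, which leaves a small, outcome-related subset for the response–mutation comparison and conflicts with other sections on who is typed

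*Combined protocol and SAP*

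**What the plan says.** Six places bear on who has tumour PTCH1 typed.

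- **Section 2.2** sets the condition "If tumor removal is required, to assess tumor" on PTCH1 assessment both before and after treatment, in both cohorts. The purpose is "in order to determine the correlation of tumor response and the presence of tumor" PTCH1 mutation. The germline objective in the same section covers NBCCS patients only.
- **Section 4.4, Biopsy and Analysis of the Tumor**: where a previous biopsy exists, "a tissue slide will be obtained for study purposes and confirmation of KCOT diagnosis". For mutation and expression analysis, if there is no additional fresh-frozen specimen, "the initial biopsy samples, which are formalin-fixed, paraffin-embedded (FFPE), will be used instead". DNA may come from frozen or FFPE sections. The same subsection calls storage of leftover tumour for future genetic analysis optional.
- **Section 4.4.2** lists tumour genetic testing at the baseline visit, with a qualifier about biopsy and excision that is hard to parse. It also obtains diagnostic slides, or a biopsy where there is none.
- **Section 4.4.3** lists tumour testing at 1 year with no removal condition.
- **Appendix A** has the row "Genetic Testing of the Tumor, if biopsy on excision", marked at baseline, 1 year and discontinuation.
- **Section 4.8 b.iv**: the effect of the PTCH1 "mutation on tumor volume reduction will be assessed with an independent samples t-test". It adds "These analyses will use the same population as the primary endpoint". It does not say whether germline or tumour status is meant.

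On removal itself, section 4.1.1 requires "Willingness to delay excision of the target tumor site, unless evidence of disease progression or lack of drug tolerability". Section 1.1 hopes that shrinkage will reduce the extent of surgery or remove the need for it.

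**The concern.** In section 2.2, whether the explanatory variable is measured depends on an event after treatment that is linked to the outcome. Progression is a trigger for excision, and a good response may avoid surgery. The better the drug works, the fewer responders are typed. If nobody needs removal, the objective as worded yields no data.

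Two things follow. The number analysed falls, and any selection on poor response pulls the mutant versus non-mutant difference toward zero. A real PTCH1 effect could then be reported as absent. Sporadic patients are the most exposed, because section 2.2 gives them no germline objective.

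The t-test in section 4.8 b.iv cannot use the primary-endpoint population if tumour status exists only for removed tumours. The missing-data rules in section 4.8 replace or estimate missing observations and say nothing about patients without a mutation result.

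**Working it through.** **1. The plan's own power figure.** Section 4.8 b.v gives detectable changes of about 1.0 SD (n = 10) and 0.68 SD (n = 20) for the Wilcoxon signed-rank test, two-sided 5%, 80% power. Using a one-sample noncentral t with n multiplied by 3/π (effective n 9.55 and 19.10), I get 1.027 and 0.678 SD. Simulated Wilcoxon power at the stated values is 0.786 and 0.803. The figure reproduces, but it concerns the primary endpoint. No power statement is given for the PTCH1 comparison.

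**2. Expected split.** Section 1.1 gives mutation rates of 88% (NBCCS) and 29% (sporadic). In 10 + 10 patients this is 10 × 0.88 + 10 × 0.29 = 11.7 mutated, or roughly 12 against 8.

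**3. Detectable difference without any selection.** Two-sample t-test, noncentrality d × √(n1·n2/(n1 + n2)), two-sided 5%, 80% power. The numbers removed are assumed, because the documents give no removal rate.

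| Typed | Split | √(n1·n2/(n1+n2)) | Detectable d |
|---|---|---|---|
| 20 | 12/8 | √4.8 = 2.19 | 1.36 SD |
| 10 | 6/4 | √2.4 = 1.55 | 2.1 SD |
| 8 | 5/3 | √1.875 = 1.37 | 2.5 SD |
| 5 | 3/2 | √1.2 = 1.10 | 3.9 SD |

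**4. Adding selection.** Assumed model: response Y = d × M + N(0,1), where M is mutation status. The removal score is −ρ × (standardised Y) + √(1 − ρ²) × N(0,1), and the patients with the highest scores are removed and typed. Here ρ is the correlation between removal and poor response. A simulated trial with fewer than two patients in either group counts as no detection. Power at d = 1.5 SD:

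| Typed | ρ = 0 | ρ = 0.6 | ρ = 1 |
|---|---|---|---|
| 20 (all) | about 86% | – | – |
| 10 | about 50% | about 44% | about 16% |
| 6 | about 22% | about 17% | about 3% |

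With 10 typed and ρ = 1 the loss is 86 − 16 = 70 points. Of these, 86 − 50 = 36 come from the smaller number alone and 50 − 16 = 34 from selection. At ρ = 0.6 selection adds only 50 − 44 = 6 points. With 6 typed, about 23% (ρ = 0) to 65% (ρ = 1) of simulated trials lack two patients per group, which explains much of the very low figure.

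**5. Size of the attenuation.** A true 1.0 SD difference becomes about 0.77–0.81 SD at ρ = 0.6 and 0.27–0.39 SD at ρ = 1, with 30–50% removed. Over a wider range (d 0.5–1.5 SD, 25–75% removed) the share of the difference that remains is:

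- ρ = 0: all of it
- ρ = 0.3: 0.93–0.97
- ρ = 0.6: 0.74–0.89
- ρ = 0.9: 0.39–0.71
- ρ = 1: 0.24–0.63

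If there is no true effect, selection creates none.

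**The case against.** The strongest reply is that the protocol already provides tumour status without removal. Section 4.4 falls back on the initial FFPE biopsy, section 4.4.2 and Appendix A place tumour testing at baseline before any drug is given, and section 4.8 b.iv names the full population. Section 2.2 can be read as concerning mainly the paired before/after assessment, which does need post-treatment tissue. This stands as a possible reading, but not as a commitment. Section 2.2 applies its condition to the before-treatment assessment and to the response correlation. The baseline entries carry the unclear biopsy/excision qualifier. Section 4.4 also presents stored tumour tissue as optional and for future use.

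A reader might infer that the correlation will be estimated only in poor responders and will be strongly attenuated. The documents do not support that. Lack of tolerability is also an excision trigger and is not a measure of response. Section 1.1 foresees smaller surgery after shrinkage, so partial responders may still be operated on. The plan neither defines when removal is required nor gives a removal rate. Strong attenuation appears only when poor response decides removal almost entirely.

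It is also fair that full typing does not make the comparison well powered. At a true 1.0 SD difference, power with all 20 typed is about 53%.

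**Conclusion.** The concern holds as a conflict between sections with a probable statistical cost. If section 2.2 is followed, the response–mutation comparison rests on a small, outcome-related subset that cannot be the population named in section 4.8 b.iv. The loss of precision does not depend on tight selection: at a true 1.5 SD difference, power falls from about 86% to about 50% with 10 typed, or 22% with 6, even if removal is unrelated to response. Attenuation is likely in direction, but its size is not fixed by the documents. It ranges from none to most of the effect, depending on how closely removal follows poor response.

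These figures assume a normal response, mutation rates of 88% and 29%, and chosen values for the effect, the number removed and the removal/response correlation. The objective is secondary, so the change should be made but does not threaten the primary analysis. It is best made early, because tissue and consent may not be recoverable later.

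**What to change.** - In sections 2.2 and 4.4.2 and Appendix A, state that pre-treatment tumour PTCH1 is typed for every treated patient with usable tissue, from the diagnostic FFPE slide or biopsy already obtained, using the DNA method in section 4.4.
- In section 4.8 b.iv, say that the t-test uses this pre-treatment tumour status and not germline status.
- Keep the removal condition only for the before/after mutation comparison, and report that comparison descriptively.
- Align sections 2.2, 4.4, 4.4.2, 4.4.3, 4.8 b.iv and Appendix A, including the unclear biopsy/excision wording and the optional status of tumour genetics.
- Report how many patients were typed, and whether the tissue came from the treated lesion or an earlier one.

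The cost is about 20 assays plus protocol and consent wording, with no new biopsy. Some archived samples will fail or be unavailable, since section 4.1.1 accepts a past pathology report. Some will come from an earlier lesion, because eligible tumours are recurrent. In patients with multiple tumours and no earlier biopsy, only selected lesions are biopsied. These losses should not depend on response to the study drug.

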## 3. STUDY DESIGN

### 3.1 Description of the Study

This is a single-center, interventional, single-arm, open-label, two-cohort clinical trial. A total of 40 patients will be screened in order for 20 patients to be enrolled (10 with NBCCS-associated KCOT and 10 with sporadic KCOT) over a period of 2 years. This is a 3 year study where each patient will undergo up to 1 year of treatment and up to 2 years of post-treatment follow-up. If a patient is experiencing an ongoing adverse event at the time of the study completion, he/she will be followed-up until resolution of the adverse event or until the condition has stabilized. The same applies to patients who are withdrawn from the study due to adverse events.

It is estimated that it will take approximately 2 years to recruit 20 patients for the study (10 with NBCCS-associated KCOT and 10 with sporadic KCOT).

All patients will be assessed for safety and efficacy of the study drug GDC-0449 (Vismodegib).

